	Grade 3 or 4 (Grade 3: Serum Creatinine > 3.0 X baseline; >3.0-6.0 X ULN  Grade 4: Serum Creatinine > 6.0 X ULN)	Permanently discontinue study drug/study regimen	
 
Carefully monitor serum creatinine on daily basis
 
Consult Nephrologist and consider renal biopsy if clinically indicated
 
Promptly start prednisone 1 to 2 mg/kg/day PO or IV equivalent
 
If event is not responsive within 3-5 days or worsens despite prednisone at 1-2 mg/kg/day PO or IV equivalent, additional workup should be considered and prompt treatment with IV methylprednisolone 2-4mg/kg/day started.
 
Once improving, gradually taper steroids over ≥28 days and consider prophylactic antibiotics, antifungals and anti PCP treatment (please refer to current NCCN guidelines for treatment of cancer-related infections [Category 2B recommendation]
 

Rash (excluding Bullous skin formations)	Grade of Skin Rash (Please refer to NCI CTCAE version 4.03 for definition of severity/grade depending on type of skin rash) Grade 1	No dose modification	Monitor for signs and symptoms of dermatitis (rash and pruritus)  **IF THERE IS ANY BULLOUS FORMATION, THE STUDY PHYSICIAN SHOULD BE CONTACTED AND STUDY DRUG DISCONTINUED**  For Grade 1:
	Grade 2	For persistent (> 1- 2 weeks) Grade 2 events, hold scheduled study drug/study regimen	
 
Consider symptomatic treatment including oral antipruritics (eg, diphenhydramine or hydroxyzine) and topical therapy (eg, urea cream)
 
For Grade 2:
 
Obtain dermatology consult
 

	Immune-Mediated Reaction	ns
	Dose Modifications	Toxicity Management
	
 
until resolution to ≤ Grade 1 or baseline
 
If toxicity worsens then treat as Grade 3
 
If toxicity improves to ≤ Grade 1 or baseline then resume study drug/study regimen after completion of steroid taper.
 
	
 
Consider symptomatic treatment including oral antiprurities (eg, diphenhydramine or hydroxyzine) and topical therapy (eg, urea cream)
 
Consider moderate-strength topical steroid
 
If no improvement of rash/skin lesions occurs within 3-5 days or is worsening despite symptomatic treatment and/or use of moderate strength topical steroid, discuss with study physician and promptly start systemic steroids prednisone 1-2 mg/kg/day PO or IV equivalent
 
Consider skin biopsy if persistent for >1-2 weeks or recurs
 

Grade 3	Hold study drug/study regimen until resolution to ≤ Grade 1 or baseline  If temporarily holding the study drug/study regimen does not provide improvement of the Grade 3 skin rash to ≤ Grade 1 or baseline within 30 days, then permanently discontinue Study drug/study regimen	For Grade 3 or 4:  - Consult dermatology  - Promptly initiate empiric IV methylprednisolone 1 to 4 mg/kg/day or equivalent  - Consider hospitalization  - Monitor extent of rash [Rule of Nines]  - Consider skin biopsy (preferably more than 1) as
Grade 4	Permanently discontinue study drug/study regimen	
 
clinically feasible.
 
Once improving, gradually taper steroids over ≥28 days and consider prophylactic antibiotics, antifungals and anti PCP treatment (please refer to current NCCN guidelines for treatment of cancer-related infections [Category 2B recommendation])
 
Discuss with Study Physician
 

		Immune-Mediated Reaction	ons
		Dose Modifications	Toxicity Management
Endocrinopathy (eg, hyperthyroidism, hypothyroidism, hypopituitarism, adrenal insufficiency, etc.)	Any Grade (Depending on the type of endocrinopathy, refer to NCI CTCAE version 4.03 for defining the CTC grade/severity)	General Guidance	
 
Consult Endocrinologist
 
Monitor patients for signs and symptoms of endocrinopathies. Non-specific symptoms include headache, fatigue, behavior changes, changed mental status, vertigo, abdominal pain, unusual bowel habits, hypotension and weakness.
 
Patients should be thoroughly evaluated to rule out any alternative etiology (eg, disease progression including brain metastases, infections, etc.)
 
Monitor and evaluate thyroid function tests: TSH, free T3 and free T4 and other relevant endocrine labs depending on suspected endocrinopathy.
 
If a patient experiences an AE that is thought to be possibly of autoimmune nature (eg, thyroiditis, pancreatitis, hypophysitis, diabetes insipidus), the investigator should send a blood sample for appropriate autoimmune antibody testing
 

	Grade 1 (Depending on the type of endocrinopathy, refer to NCI CTCAE version 4.03 for defining the CTC grade 1)	No dose modification	For Grade 1: (including those with asymptomatic TSH elevation)  - Monitor patient with appropriate endocrine function tests  - If TSH < 0.5 X LLN, or TSH >2X ULN or consistently out of range in 2 subsequent measurements, include FT4 at subsequent cycles as clinically indicated and consider endocrinology consult.

EDMS Doc. Number: CCI

	Immune-Mediated Reactio	ons
	Dose Modifications	Toxicity Management
Grade 2 (Depending on the type of endocrinopathy, refer to NCI CTCAE version 4.03 for defining the CTC grade/severity 2)	For Grade 2 endocrinopathy other than hypothyroidism, hold study drug/study regimen dose until subject is clinically stable  • If toxicity worsens then treat as Grade 3 or Grade 4  Study drug/study regimen can be resumed once event stabilizes and after completion of steroid taper  Patients with endocrinopathies who may require prolonged or continued steroid replacement can be retreated with study drug/study regimen on the following conditions: 1) the event stabilizes and is controlled, 2) the patient is clinically stable as per Investigator or treating physician's clinical judgement, and 3) doses of prednisone are at less than or equal to 10 mg/day or equivalent.	For Grade 2: (including those with symptomatic endocrinopathy)  - Isolated hypothyroidism may be treated with replacement therapy without treatment interruption and without corticosteroids  - Initiate hormone replacement as needed for management  - Evaluate endocrine function, and as clinically indicated, consider pituitary scan  - For patients with abnormal endocrine work up, except for those with isolated hypothyroidism, consider short-term, corticosteroids (eg, 1-2mg/kg/day methylprednisolone or IV equivalent) and prompt initiation of treatment with relevant hormone replacement (eg, Levothyroxine, hydrocortisone, or sex hormones)  - Once improving, gradually taper steroids over ≥28 days and consider prophylactic antibiotics, antifungals and anti PCP treatment (please refer to current NCCN guidelines for treatment of cancer-related infections [Category 2B recommendation])  - For patients with normal endocrine work up (lab or MRI scans), repeat labs/MRI as clinically indicated.

		Immune-Mediat	ted Reactio	ns
		Dose Modifications		Toxicity Management
	Grade 3 or 4 (Depending on the type of endocrinopathy, refer to NCI CTCAE version 4.03 for defining the CTC grade/severity 3 or 4)	For Grade 3 or 4 endocrinopathy othe hypothyroidism, hold study drug/stud regimen dose until endocrinopathy sy are controlled  Study drug/study regimen can be resu event stabilizes and after completion taper	y mptom(s)	
 
For Grade 3 or 4:         
 
Consult endocrinologist
 
Isolated hypothyroidism may be treated with replacement therapy without treatment interruption and without corticosteroids
 
Promptly initiate empiric IV methylprednisolone 1 to 2 mg/kg/day or equivalent
 
Administer hormone replacement therapy as necessary.
 
For adrenal crisis, severe dehydration, hypotension, or shock: immediately initiate intravenous corticosteroids with mineralocorticoid activity
 
Once improving, gradually taper immunosuppressive steroids over ≥28 days and consider prophylactic antibiotics, antifungals and anti PCP treatment (please refer to current NCCN guidelines for treatment of cancer-related infections [Category 2B recommendation])
 
Discuss with study physician
 
 
 

Immune mediated Neurotoxicity (to include but not limited to limbic encephalitis. autonomic neuropathy, excluding	Grade of Neurotoxicity Depending on the type of neurotoxicity, refer to NCI CTCAE version 4.03 for defining the CTC grade/severity	NE PRO		
Myasthenia Gravis and Guillain-Barre)	Any Grade	General Guidance	di	atients should be evaluated to rule out any alternative etiology (eg, sease progression, infections, metabolic syndromes and edications, etc.)

	ated Reactions	
	Dose Modifications	Toxicity Management
Grade 1	No dose modifications	
 
Monitor patient for general symptoms (headache, nausea, vertigo, behavior change, or weakness)
 
Consider appropriate diagnostic testing (eg, electromyogram and nerve conduction investigations)
 
Symptomatic treatment with neurological consult as appropriate
 
See "Any Grade" recommendations above.
 

Grade 2	
 
For acute motor neuropathies or neurotoxicity, hold study drug/study regimen dose until resolution to ≤ Grade 1
 
For sensory neuropathy/neuropathic pain, consider holding study drug/study regimen dose until resolution to ≤ Grade 1.         
 
If toxicity worsens then treat as Grade 3 or Grade 4
 
 
 
Study drug/study regimen can be resumed once event improves to ≤ Grade 1 stabilizes after completion of steroid taper
 
	
 
Discuss with the study physician
 
Obtain Neurology Consult
 
Sensory neuropathy/neuropathic pain may be managed by appropriate medications (eg, gabapentin, duloxetine, etc.)
 
Promptly start systemic steroids prednisone 1-2mg/kg/day PO or IV equivalent
 
If no improvement within 3-5 days despite 1-2mg/kg/day prednisone PO or IV equivalent consider additional workup and promptly treat with additional immunosuppressive therapy (eg, IVIG)
 

Grade 3	Hold Study drug/study regimen dose until resolution to ≤ Grade 1	For Grade 3 or 4:  - Discuss with study physician

	Immune-Mediated Reactions								
		Dose Modifications		Toxicity Management					
		• Permanently discontinue Study drug/study regimen if Grade 3 irAE does not resolve to ≤ Grade 1 within 30 days.	- - -	Obtain Neurology Consult Consider hospitalization Promptly initiate empiric IV methylprednisolone 1 to 2 mg/kg/day or equivalent If no improvement within 3-5 days despite IV corticosteroids, consider additional workup and promptly treat with additional					
	Grade 4	Permanently discontinue study drug/study regimen		immunosuppressants (eg, IVIG)  Once stable, gradually taper steroids over ≥28 days					
Immune- mediated peripheral neuromotor syndromes, such as Guillain-Barre and Myasthenia Gravis	G	General Guidance	_	The prompt diagnosis of immune-mediated peripheral neuromotor syndromes is important, since certain patients may unpredictably experience acute decompensations which can result in substantial morbidity or in the worst case, death. Special care should be taken for certain sentinel symptoms which may predict a more severe outcome, such as prominent dysphagia, rapidly progressive weakness, and signs of respiratory insufficiency or autonomic instability  Patients should be evaluated to rule out any alternative etiology (eg, disease progression, infections, metabolic syndromes and medications, etc.). It should be noted that the diagnosis of immune-mediated peripheral neuromotor syndromes can be particularly challenging in patients with underlying cancer, due to the multiple potential confounding effects of cancer (and its treatments) throughout the neuraxis. Given the importance of prompt and accurate diagnosis, it is essential to have a low threshold to obtain a neurological consult  Neurophysiologic diagnostic testing (eg, electromyogram and nerve conduction investigations, and "repetitive stimulation" if myasthenia is suspected) are routinely indicated upon suspicion of such conditions and may be best facilitated by means of a neurology consultation  Important to consider that the use of steroids as the primary treatment of Guillain-Barre is not typically considered effective.  Patients requiring treatment should be started with IVIG and followed by plasmapheresis if not responsive to IVIG					

	Immune-Media	ated Reacti	ons
	Dose Modifications		Toxicity Management
Grade 1  Grade 2	No dose modification  Hold study drug/study regimen	- (	Discuss with the study physician  Care should be taken to monitor patients for sentinel symptoms of a potential decompensation as described above  Obtain a neurology consult unless the symptoms are very minor and stable
Grade 2	Hold study drug/study regimen dose until resolution to ≤ Grade 1  Permanently discontinue study drug/study regimen if it does not resolve to ≤ Grade 1 within 30 days or if there are signs of respiratory insufficiency or autonomic instability	- I - ( - ( - (	Discuss with the study physician Care should be taken to monitor patients for sentinel symptoms of a potential decompensation as described above Dbtain a Neurology Consult Sensory neuropathy/neuropathic pain may be managed by appropriate medications (eg, gabapentin, duloxetine, etc.)  MYASTHENIA GRAVIS  Steroids may be successfully used to treat Myasthenia Gravis. Important to consider that steroid therapy (especially with high doses) may result in transient worsening of myasthenia and should typically be administered in a monitored setting under supervision of a consulting neurologist.  Patients unable to tolerate steroids may be candidates for treatment with plasmapheresis or IVIG. Such decisions are best made in consultation with a neurologist, taking into account the unique needs of each patient.  If Myasthenia Gravis-like neurotoxicity present, consider starting acetylcholine esterase (AChE) inhibitor therapy in addition to steroids. Such therapy, if successful, can also serve to reinforce the diagnosis.  GUILLAIN-BARRE:  Important to consider here that the use of steroids as the primary treatment of Guillain-Barre is not typically considered effective. Patients requiring treatment should be started with IVIG and followed by plasmapheresis if not responsive to IVIG.

	Immune-Media	iated Reactions		
	Dose Modifications	Toxicity Management		
Grade 4	Hold study drug/study regimen dose until resolution to ≤ Grade 1  Permanently discontinue Study drug/study regimen if Grade 3 irAE does not resolve to ≤ Grade 1 within 30 days or if there are signs of respiratory insufficiency or autonomic instability  Permanently discontinue study drug/study regimen	- Disc - Rec	cuss with study physician commend hospitalization nitor symptoms and obtain neurological consult  MYASTHENIA GRAVIS  Steroids may be successfully used to treat Myasthenia Gravis. It should typically be administered in a monitored setting under supervision of a consulting neurologist.  Patients unable to tolerate steroids may be candidates for treatment with plasmapheresis or IVIG.  If Myasthenia Gravis-like neurotoxicity present, consider starting acetylcholine esterase (AChE) inhibitor therapy in addition to steroids. Such therapy, if successful, can also serve to reinforce the diagnosis.  GUILLAIN-BARRE:  Important to consider here that the use of steroids as the primary treatment of Guillain-Barre is not typically considered effective. Patients requiring treatment should be started with IVIG and followed by plasmapheresis if not responsive to IVIG	

<sup>a ASCO Educational Book 2015 "Managing Immune Checkpoint Blocking Antibody Side Effects" by Michael Postow MD.

FDA Liver Guidance Document 2009 Guidance for Industry: Drug Induced Liver Injury – Premarketing Clinical Evaluation.

<sup>b NCI CTCAE version 4.03.

Appendix E-2: Durvalumab Treatment Modification and Toxicity Management Guidelines for Infusion-related Reactions

Infusion-Related Reactions								
Severity Grade	Dose Modifications	Toxicity Management						
Any Grade	General Guidance	
 
Management per institutional standard at the discretion of investigator
 
Monitor patients for signs and symptoms of infusion-related reactions (eg, fever and/or shaking chills, flushing and/or itching, alterations in heart rate and blood pressure, dyspnea or chest discomfort, skin rashes etc.) and anaphylaxis (eg, generalized urticaria, angioedema, wheezing, hypotension, tachycardia, etc.)
 
						
Grade 1	The infusion rate of study drug/study regimen may be decreased by 50% or temporarily interrupted until resolution of the event	For Grade 1 or Grade 2:  - Acetaminophen and/or antihistamines may be administered per institutional standard at the discretion of the investigator						
Grade 2	The infusion rate of study drug/study regimen may be decreased 50% or temporarily interrupted until resolution of the event  Subsequent infusions may be given at 50% of the initial infusion rate	
 
Consider premedication per institutional standard prior to subsequent doses
 
Steroids should not be used for routine premedication of ≤Grade 2 infusion reactions.
 
						
Grade 3/4	Permanently discontinue study drug/study regimen	For Grade 3 or 4:  Manage severe infusion-related reactions per institutional standards (eg, IM epinephrine, followed by IV diphenhydramine and ranitidine, and IV glucocorticoid)						

Appendix E-3: Durvalumab Treatment Modification and Toxicity Management Guidelines for Non-immune-mediated Reactions

	Non-immune Mediated Reactions	
(Note: As applicable, for	or early phase studies, the following sentence may be added: "Any event greater than or equal to	Grade 2, please discuss with Study Physician"
Severity Grade of the Event (NCI CTCAE version 4.03)	Dose Modification	Toxicity Management
Any Grade	Note: dose modifications are not required for adverse events not deemed to be related to study treatment (ie, events due to underlying disease) or for laboratory abnormalities not deemed to be clinically significant.	Treat accordingly as per institutional standard
1	No dose adjustment	Treat accordingly as per institutional standard
2	Hold study drug/study regimen until resolution to ≤ Grade 1 or baseline	Treat accordingly as per institutional standard
3	Hold study drug/study regimen until resolution to ≤ Grade 1 or baseline  For AEs that downgrade to ≤ Grade 2 within 7 days or resolve to ≤ Grade 1 or baseline within 14 days, resume study drug/study regimen administration. Otherwise, discontinue study drug/study regimen	Treat accordingly as per institutional standard
4	Discontinue Study drug/study regimen (Note for Grade 4 labs, decision to discontinue would be based on accompanying clinical signs/symptoms and as per Investigator's clinical judgment and in consultation with the Sponsor)	Treat accordingly as per institutional standard

AChE = acetylcholine esterase; ADA = American Dietetic Association; ADL= activity of daily life; AE = adverse event; ALP = alkaline phosphatase; ALT = alanine aminotransferase; AST = aspartate aminotransferase; BUN= blood urea nitrogen; CT = computed tomography; CTC= common terminology criteria; GI = gastrointestinal; FT4= free T4; ILD = interstitial lung disease; IM = intramuscular; irAE = immune-related adverse event; IV = intravenous; LFT= liver function tests; LLN= lower level normal; MRI=magnetic resonance imaging; NCI CTCAE = National Cancer Institute Common Terminology Criteria for Adverse Events; PO = by mouth; TB= total bilirubin; TNF = tumor necrosis factor; TSH = thyroid stimulating hormone; ULN = upper limit of normal.

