Immune-Mediated Reactions		
	Dose Modifications	Toxicity Management
Grade 1 [Serum Creatinine > 1-1.5 X baseline; > ULN to 1.5 X ULN]	No dose modification	For Grade 1 elevated creatinine:  - Monitor serum creatinine weekly and any accompanying symptom  • If creatinine returns to baseline, resume its regular monitoring per study protocol.  • If it worsens, depending on the severity, treat as Grade 2 or Grade 3 or 4  - Consider symptomatic treatment including hydration, electrolyte replacement, diuretics, etc.
Grade 2 [Serum Creatinine>1.5-3.0 X baseline; >1.5 X- 3.0 X ULN]	
 
Hold study drug/study regimen until resolution to ≤ Grade 1 or baseline
 
If toxicity worsens then treat as Grade 3 or Grade 4
 
If toxicity improves to ≤ Grade 1 or baseline then resume study drug/study regimen after completion of steroid taper.
 
	
 
For Grade 2 elevated creatinine:         
 
Consider symptomatic treatment including hydration, electrolyte replacement, diuretics, etc.
 
Carefully monitor serum creatinine every 2-3 days and as clinically warranted
 
Consult Nephrologist and consider renal biopsy if clinically indicated
 
If event is persistent (> 3-5 days) or worsens, promptly start prednisone 1 to 2 mg/kg/day PO or IV equivalent
 
If event is not responsive within 3-5 days or worsens despite prednisone at 1-2 mg/kg/day PO or IV equivalent, additional workup should be considered and prompt treatment with IV methylprednisolone at 2-4mg/kg/day started.
 
Once improving gradually taper steroids over ≥28 days and consider prophylactic antibiotics, antifungals and anti PCP treatment (please refer to current NCCN guidelines for treatment of cancer-related infections [Category 2B recommendation]).
 
When event returns to baseline, resume study drug/study regimen and routine serum creatinine monitoring per study protocol.
 
 
 

		Immune-Mediated Reaction	ons
		Dose Modifications	Toxicity Management

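### The Grade 2 creatinine row of Appendix E-1 gives two restart instructions for study drug, and they conflict for a subject back at baseline whose steroid taper is still running

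*Protocol*

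**What the plan says.** All the relevant text is current and sits in the Nephritis or Renal Dysfunction block of Appendix E-1.

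- **Grade 2, Dose Modifications, hold:** "Hold study drug/study regimen until resolution to ≤ Grade 1 or baseline".
- **Grade 2, Dose Modifications, restart:** "If toxicity improves to ≤ Grade 1 or baseline then resume study drug/study regimen after completion of steroid taper".
- **Grade 2, Toxicity Management, taper:** "Once improving gradually taper steroids over ≥28 days".
- **Grade 2, Toxicity Management, restart:** "When event returns to baseline, resume study drug/study regimen and routine serum creatinine monitoring per study protocol".
- **Grade definitions:** "Grade 1 [Serum Creatinine > 1-1.5 X baseline; > ULN to 1.5 X ULN" and "Grade 2 [Serum Creatinine>1.5-3.0 X baseline; >1.5 X- 3.0 X ULN".
- **Grade 1, Toxicity Management:** "If creatinine returns to baseline, resume its regular monitoring per study protocol".

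Protocol Section 7.2.4.1 sends sites to Appendix E for DURVA dose modification and does not say which column governs. The note that opens Appendix E describes the tables as an aid to the investigator's clinical judgment. The SAP does not address restart rules.

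**The concern.** One row states the restart rule twice, and the two statements differ in two respects. The first makes completion of the steroid taper a condition and the second does not mention it. The first accepts Grade 1 or baseline and the second names baseline only.

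The taper difference matters more. A site following the Toxicity Management column could give DURVA to a subject still on steroids for a suspected immune-related renal event. A site following the Dose Modifications column would wait. Treatment of the same subject would then depend on which column was read. The same choice would feed into the DURVA relative dose intensity and dose delay summaries (SAP Sections 9.6 and 9.7) and into the setting in which nephritis and creatinine increases, an event of special interest in SAP Section 11.2, are observed.

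**Working it through.** The plan gives no figure to reproduce here. The check compares the two texts and then works out the timing.

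**Step 1: is baseline shorthand for Grade 1 or less?** No. Grade 1 is "Serum Creatinine > 1-1.5 X baseline; > ULN to 1.5 X ULN", so by the baseline limb it lies above baseline and runs to 1.5 times it. The Grade 1 row treats return to baseline as a further step down. The Dose Modifications sentence lists Grade 1 and baseline as alternatives.

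**Step 2: apply each column to every state.**

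| Creatinine | Taper | Dose Modifications | Toxicity Management |
|---|---|---|---|
| Grade 2 | running | hold | trigger not met |
| Grade 2 | complete or not needed | hold | trigger not met |
| Grade 1, above baseline | running | hold | trigger not met |
| Grade 1, above baseline | complete or not needed | resume | trigger not met |
| Baseline | running | hold | resume |
| Baseline | complete or not needed | resume | resume |

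The fifth line is an express conflict. The fourth is a difference in the stated level. With an assumed baseline of 1.0 mg/dL, recovery to 1.3 mg/dL is 1.3 / 1.0 = 1.3 times baseline, which is Grade 1, so only the first column's condition is met. The other four lines agree.

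**Step 3: size of the conflict in the fifth line.** Inputs:

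- DURVA is given once per 28-day cycle, on Day 1 from Cycle 2 (Section 7.2.2.1), so the next planned dose is Day 29.
- When treatment is interrupted and the next cycle is delayed, its Day 1 becomes the day treatment resumes (Section 7.2.4).
- The taper lasts at least 28 days (Appendix E-1); 28 is used.
- Assumptions: the event begins on cycle day d after that cycle's dose has been given, baseline is regained 7 days later, the taper starts then, and the dose is given as soon as it is both due and permitted. Visit windows are ignored.

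Formulas:

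- Toxicity Management: next dose on day max(29, d + 7).
- Dose Modifications: next dose on day d + 7 + 28 = d + 35.
- Difference: (d + 35) − max(29, d + 7).

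Results:

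- d = 1: Day 36 versus Day 29, a difference of 7 days.
- d = 22: Day 57 versus Day 29, a difference of 28 days.
- d = 28: Day 63 versus Day 35, a difference of 28 days.

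**Step 4: sensitivity.** If the taper began before baseline was regained, the gap shrinks. For example, with baseline reached on day 14 of a 28-day taper, 28 − 14 = 14 days of taper remain. A longer taper widens the gap. If a site kept DURVA to the original calendar (Days 29, 57, 85), the gap would be 28 days at both ends: Day 29 versus Day 57 for d = 1, and Day 57 versus Day 85 for d = 28.

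**The case against.** **The second column states a trigger, not a hold.** The only hold in the row is in the Dose Modifications column, and it ends at Grade 1 or baseline. A reader might infer that a subject who settles at 1.3 times baseline with the taper finished must stay off DURVA without limit. The text does not support that: it would require reading a sufficient condition for restarting as a necessary one. This objection stands, and it reduces the difference in creatinine level to a secondary ambiguity.

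**The bullets can be read in order.** The taper bullet comes immediately before the restart bullet, most other immune-related rows that allow a restart require the taper to be complete, and the explicit dosing rule sits under the dosing heading. A careful site might reach a single reading this way. But the restart bullet is tied to the creatinine value, the taper bullet says when tapering begins rather than that dosing waits for its end, and no text ranks the columns. The other organ-specific Grade 2 rows have no restart sentence in the Toxicity Management column, so this row is an exception.

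**The effect is a delay.** A reader might infer that at least one DURVA dose is always lost. Section 7.2.4 allows the cycle to restart when treatment resumes, so for a minimum-length taper 28 days is the top of the range in Step 3, not the floor. This stands.

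**The tables are guidance.** That lowers the consequence but does not reconcile the sentences, and Section 7.2.4.1 relies on the appendix for the detail.

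**Conclusion.** The point holds for the steroid-taper condition. For a subject on steroids who is back at baseline before the taper ends, the row gives opposite instructions. On the stated assumptions the next DURVA dose differs by about 7 to 28 days. The naming of two creatinine levels is a lesser ambiguity in the same row.

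The conflict arises only in subjects given steroids, which the row starts when the event persists beyond 3 to 5 days or worsens. Without steroids, only the difference in level remains. The documents give no expected frequency for these events, so the number of subjects affected cannot be estimated. A reader might also infer that the entry limit on creatinine clearance makes this worse, but nothing in the documents links that limit to the conflict.

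This is a drafting inconsistency in a dosing rule with a safety bearing. It does not touch the overall response rate, the decision rules, the sample size or the error rates. This review takes no position on which restart condition is right.

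**What to change.** Reconcile the two columns of the Grade 2 creatinine row so that it states one creatinine level and one steroid-taper condition for restarting study drug. The sponsor's safety physician should decide both. The Toxicity Management bullet should not simply be deleted, because it also carries this row's instruction on returning to routine creatinine monitoring, which should be kept. Notify sites of the reconciled wording.

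The cost is about one sentence in Appendix E-1 at the next amendment and a letter to sites. No data collection, sample size or analysis changes.
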